## 5 General Considerations

The derivation of PK parameters will be performed by the IMPAACT 2017 protocol pharmacologists, as described in the PK SAP. The statistical summaries to be prepared by the statisticians are described in this Primary SAP.

Continuous variables will be summarized by N, N missing, mean, standard deviation, and quantiles of minimum, 25th percentile, median, 75th percentile, and maximum. Categorical variables will be summarized by N (%) in each category, excluding the missing category in the denominator.

For all baseline demographics and exposure analyses, results will be presented for the All Treated analysis set. The baseline value will be the latest pre-dose assessment with a non-missing value, including those from unscheduled visits. If time is not collected, Day 1 assessments are assumed to be taken prior to first dose and used as baseline. Unless otherwise stated, if baseline data are missing, no derivation will be performed and baseline will be set to missing.

All safety data will be considered from the first patient exposure to study treatment. Each participant's safety data will be summarized as: (1) the worst grade of each AE and (2) the worst grade of each AE judged to be related to study treatment.

Listings of all Grade 3 or higher AEs regardless of treatment attribution, serious AEs meeting ICH criteria assessed as related to study product(s), and AEs which resulted in permanent discontinuation of study product(s) or death will be provided. These categories of AEs will also be summarized and broken down by System Organ Class. The Division of AIDS Table for Grading the Severity of Adult and Pediatric Adverse Events (DAIDS AE Grading Table), Corrected Version 2.1, dated July 2017, will be used in this study. This table is available on the RSC website at <https://rsc.niaid.nih.gov/clinical-research-sites/daids-adverse-event-grading-tables>.

Analyses of primary and secondary outcome measures will include Cohort 1-naïve evaluable participants, as defined above. Supplementary analyses of safety and virologic outcome measures will include all participants (Cohort 1-naïve and Cohort 1 rollovers) who received study products (All Treated analysis set referenced above).

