#### **6.2.2 Virologic Estimands**

Secondary Objective 3: To assess antiviral activity of CAB LA + RPV LA in adolescents living with HIV who are virologically suppressed through Week 24 and through Week 48 (Cohort 2A: oral followed by injectable)/through Week 20 and through Week 44 (Cohort 2B: injectable only).	
Estimand	Probability of a virologically suppressed adolescent (aged 12 to <18 years) living with HIV-1, who was either exclusively treated with the combination of RPV and CAB at the final recommended dose for 24 weeks (for oral lead-in) or 20 weeks (for direct to injection), experienced a severe, potentially life-threatening, or death event attributable to CAB and/or RPV, or permanently discontinued CAB and/or RPV due to a related toxicity, having virologic failure (plasma HIV-1 RNA $\geq$ 50 copies/mL; plasma HIV-1 RNA $\geq$ 200 copies/mL) through 24/48 weeks (for oral lead-in) or 20/44 weeks (for direct to injection).
Treatment	30 mg CAB + 25 mg RPV once daily orally for four weeks followed by IM injections of 600 mg CAB LA + 900 mg RPV LA (first and second injections four weeks apart with subsequent injections every eight weeks) or direct to IM injections of 600 mg CAB LA + 900 mg RPV LA (first and second injections four weeks apart with subsequent injections every eight weeks).
Target population	Analysis set

Virologically suppressed children and adolescents 12 to <18 years of age living with HIV-1 exclusively treated with the combination of RPV and CAB at the final recommended dose for either 24/48 weeks (for oral lead-in) or 20/44 weeks (for direct to injection).
	
Participants who are exclusively treated with the combination of RPV and CAB at the final recommended dose and either completed all treatment regimen through the Week 24/48 (Cohort 2A)/Week 40/44 (Cohort 2B) visit or experienced any of the following:
 
 
• death that is attributable to the study product(s), OR
 
• study product-related Grade 3 or higher adverse event (excluding injection-site AEs), OR
 
• permanent discontinuation from treatment due to study product-related toxicities (regardless of grade) during these weeks of treatment.
 

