
Variable(s)
 
Occurrence of virologic failure through 24/48 weeks (oral lead in)/through 20/44 weeks (direct to injection):
 
 
• Plasma HIV-1 RNA <math>\geq</math>50 copies/mL
 
• Plasma HIV-1 RNA <math>\geq</math>200 copies/mL
 
	
Outcome measure(s)
 
Occurrence of virologic failure through Week 24 and through Week 48 (Cohort 2A)/through Week 20 and through Week 44 (Cohort 2B):
 
 
• Plasma HIV-1 RNA <math>\geq</math>50 copies/mL, per snapshot algorithm
 
• Plasma HIV-1 RNA <math>\geq</math>200 copies/mL, per snapshot algorithm
 

Handling of intercurrent events
 
The following intercurrent events are relevant to the estimand:
 
 
1. Discontinuation of CAB and/or RPV due to toxicity
 
2. Death related to CAB and/or RPV
 
 
These intercurrent events (1, 2) will be addressed as specified in the snapshot algorithm.
 
 
3. Discontinuation of CAB and/or RPV due to non-toxicity reasons
 
	
Handling of missing data
 
Missing data will be handled as described in the snapshot algorithm.

4. Death unrelated to CAB and/or RPV  These intercurrent events (3, 4) will be addressed using a principal stratum approach.	
Population-level summary measure	Analysis approach

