#### Supplementary Analyses

Supplementary analyses for the secondary virologic outcome measures will include all participants (Cohort 1-naïve and Cohort 1 rollovers) who received study products. All intercurrent

events and missing data will be handled as described in the snapshot algorithm. The sensitivity analyses described above will be implemented.

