

- Safety reasons (e.g. AE/death, liver chemistry stopping criteria, renal toxicity withdrawal criteria, QTc withdrawal criteria et al, as recorded in eCRF Conclusion form)

- Non-safety related reasons (e.g. Lack of efficacy, protocol deviation, withdrew consent, loss to follow-up, study closed/terminated, investigator discretion et al, as recorded in eCRF Conclusion Form)

	No virologic data at Week 24 Window	Disc due to AE/death

o Last on-treatment VL <200 c/mL OR no on-treatment VL available during study

	No virologic Data at Week 24 Window	Disc for other reasons

o Last on-treatment VL <math>\geq</math> 200 c/mL AND withdrawal due to Lack of efficacy

	HIV1-RNA $\geq$ 200	Disc. for lack of efficacy

o Last on-treatment VL <math>\geq</math> 200 c/mL AND withdrawal due to all other non-safety related reasons

	HIV1-RNA $\geq$ 200	Dis. for other reason and HIV-1 RNA $\geq$ 200 copies/mL

Note the same process will be mapped out for Week 48.

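### The main virologic analysis in Section 6.2.2 excludes participants who stop CAB/RPV early for lack of efficacy or while viraemic, although the snapshot algorithm that defines the outcome scores them as failures.

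*SAP*

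**What the plan says.** Antiviral activity is a secondary objective for Cohort 2 (Section 2.3.2). The outcome is HIV-1 RNA at or above 50, and at or above 200, copies/mL as classified by the snapshot algorithm (Section 3.2).

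- **Main set.** Section 5: "Analyses of primary and secondary outcome measures will include Cohort 1-naïve evaluable participants, as defined above".
- **Entry to the virologic set.** The analysis-set cell of Section 6.2.2 requires that the participant "completed all treatment regimen through the Week 24/48 (Cohort 2A)/Week 40/44 (Cohort 2B) visit or experienced any of the following". The listed events are an attributable death, a related Grade 3 or higher adverse event other than an injection-site event, and "permanent discontinuation from treatment due to study product-related toxicities (regardless of grade) during these weeks of treatment".
- **Intercurrent events.** Section 6.2.2 sends toxicity discontinuation and related death to the snapshot algorithm. Event 3 is "Discontinuation of CAB and/or RPV due to non-toxicity reasons" and event 4 is unrelated death. For these: "These intercurrent events (3, 4) will be addressed using a principal stratum approach". No exception is made for lack of efficacy.
- **Snapshot algorithm.** Attachment 2 has a withdrawal category headed "Non-safety related reasons (e.g. Lack of efficacy, protocol deviation, withdrew consent, loss to follow-up". Within it, the row "200 c/mL AND withdrawal due to Lack of efficacy" is scored as failure when the last on-treatment viral load is at or above the cut-off. So is withdrawal for any other non-safety reason with such a viral load. The guidance examples at the 50 copies/mL cut-off classify both kinds of case the same way.
- **Supplementary analysis.** For the virologic outcomes it "will include all participants (Cohort 1-naïve and Cohort 1 rollovers) who received study products", with all intercurrent events handled by the snapshot algorithm.

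**The concern.** The outcome definition and the analysis set pull against each other. The snapshot algorithm has rows written to capture people who leave because treatment failed, or who leave while viraemic. The analysis set removes nearly all of those people before the algorithm is applied, so membership of the set depends partly on the outcome being estimated.

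Stopping because of rebound is itself information about whether suppression is maintained, and maintained suppression is part of the Cohort 2 hypothesis in Section 2.2. A main estimate that does not change with the number of efficacy-driven stops cannot fully answer that question. The excluded group need not be small: Section 2.1 plans up to 100 naïve enrolments to obtain about 70 evaluable.

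**Working it through.** **Step 1. Trace one participant.** Take a Cohort 1-naïve adolescent who rebounds above the cut-off, stops CAB/RPV for lack of efficacy before the analysis visit, and has no related Grade 3 or higher event.

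| Rule | Result |
|---|---|
| Section 6.2.2 analysis set, completion route | Not met |
| Section 6.2.2 analysis set, related-event routes | Not met |
| Section 6.2.2 event 3 (non-toxicity discontinuation) | Principal stratum, so outside the set |
| Attachment 2, lack-of-efficacy row | Failure |

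Replacing lack of efficacy by, say, withdrawn consent with a last viral load at or above the cut-off gives the same conflict.

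**Step 2. Look for a planned analysis that repairs it.** The quantification-limit and missing-data sensitivity analyses in Section 6.2.2 change values or impute missing visits; neither is stated to widen the main set. Only the supplementary analysis brings these participants back, and it is specified for naïve and rollover participants together.

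**Step 3. Reproduce the plan's own figures.** Clopper-Pearson limits for x events in n are: lower = Beta quantile(0.025; x, n−x+1), upper = Beta quantile(0.975; x+1, n−x). With x = 0 the upper limit is 1 − 0.025^(1/n).

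| x/n | Computed | SAP Table 1 |
|---|---|---|
| 0/70 | 0 to 0.0513 | 0.00, 0.05 |
| 0/100 | 0 to 0.0362 | 0.00, 0.04 |
| 14/70 | 0.1139 to 0.3127 | 0.11, 0.31 |
| 20/100 | 0.1267 to 0.2918 | 0.13, 0.29 |

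All four agree. Table 1 concerns adverse events. I assume that the same interval applies to the virologic proportions, because the analysis-approach cell of the virologic table was not in the text at hand.

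**Step 4. Illustrate the size.** From Section 2.1: about 70 evaluable and up to 100 naïve. Assumed, because the SAP gives no rate: k stoppers of the kind in Step 1, no failures among the 70, and all 100 enrolled and treated.

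| k | As planned | Stoppers added back, k/(70+k) | All naïve, k/100 |
|---|---|---|---|
| 1 | 0/70 = 0% (0 to 5.1%) | 1/71 = 1.4% (0.04 to 7.6%) | 1.0% (0.03 to 5.4%) |
| 3 | 0/70 = 0% (0 to 5.1%) | 3/73 = 4.1% (0.9 to 11.5%) | 3.0% (0.6 to 8.5%) |
| 5 | 0/70 = 0% (0 to 5.1%) | 5/75 = 6.7% (2.2 to 14.9%) | 5.0% (1.6 to 11.3%) |

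The planned column is the same for every k. If 55 rollovers are pooled in and none fails, k = 3 gives 3/155 = 1.9%.

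**Step 5. Check the direction.** Let f be the failures among the 70 and k the failures among the other 30. The all-naïve proportion exceeds the planned one when (f+k)/100 > f/70, which is the same as k/30 > f/70. With f = 3 and k = 1 the plan gives 3/70 = 4.3% and all naïve gives 4/100 = 4.0%, so the planned figure is the higher. The reason is that early withdrawals who are suppressed stay in the snapshot denominator as having no virologic data, and the evaluable restriction removes them too.

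**The case against.** The strongest reply is that the SAP already reports these failures. The supplementary All Treated analysis applies the snapshot algorithm to every intercurrent event and repeats the sensitivity analyses, and a later implementation plan may show naïve and rollover participants separately. This stands in part: the failures will not be lost from the report. But the SAP does not itself specify a naïve-only result in all treated participants, and the analysis designated as main is still the one that omits them.

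Some stronger readings are tempting, and the document does not support them:

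- **That the trial's headline result is affected.** The primary objective and outcomes are safety; this is the main analysis of a secondary outcome.
- **That virologic failures in general are deleted.** Viraemia in participants who complete treatment to the visit still counts. A stopper who also has a qualifying related event stays in the set and is classified by the snapshot.
- **That the estimate is always biased towards zero.** Step 5 shows that the direction depends on the mix of excluded participants.
- **That participants covered by oral bridging are dropped.** Section 4 keeps anyone who received the recommended number of injections, even outside the window.
- **That exclusion through Week 48/44 is settled.** The Evaluable definition in Section 4 and the estimand statement in Section 6.2.2 run only to Week 24/20. On that wording, someone who passes that visit and then stops for lack of efficacy stays in. The analysis-set cell and the principal-stratum rule point the other way.

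It is also fair to say that nothing here shows a principal stratum to be wrong for unrelated death or for withdrawal while suppressed. The defect concerns lack-of-efficacy and viraemic discontinuation.

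**Conclusion.** The point holds in this form. By the SAP's own rules, the main virologic analysis leaves out naïve participants who stop before the visit for lack of efficacy, or for another non-safety reason while viraemic, unless they also have a qualifying related event. The algorithm that defines the outcome would count them as failures. This conclusion rests on the text for Week 24/20. For Week 48/44 it also depends on which of the two conflicting definitions of the set is meant.

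The size is illustrative. With 1 to 5 such stoppers and no other failures, the main result stays at 0% (upper limit 5.1%). Adding the stoppers back gives 1.4% to 6.7%, and using all 100 naïve participants gives 1.0% to 5.0%. The stopper counts, the absence of other failures and full enrolment are assumptions.

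**What to change.** In Section 6.2.2, and in Section 5 as far as it concerns virologic outcomes, handle lack-of-efficacy and viraemic discontinuation by the snapshot algorithm and keep these participants in the main set. The simplest way is to make all treated Cohort 1-naïve participants the main virologic set, since both groups are already defined in Section 4, and to report the Evaluable result as supplementary. A narrower alternative is to carve these discontinuations out of event 3 and add them to the routes into the analysis set.

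Also reconcile the Week 24/20 limit in the Section 4 Evaluable definition and in the Section 6.2.2 estimand statement with the Week 24/48 and Week 40/44 wording of the analysis-set cell. The rest of the virologic table uses Week 20/44 for Cohort 2B.

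The cost is SAP wording and one population flag. No new data are needed. The failure proportion may become less favourable.

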### Sensitivity Analyses

#### *Lower Limit of Quantification*

To correspond with the Cohort 1 primary analysis, results in the form of “< Lower Limit of Quantification” will be imputed as lower limit of quantification (LLoQ) – 1. For HIV-1 RNA results where the LLoQ is greater than the cut-off value (e.g., 60 copies/mL), we will perform four sensitivity analyses:

- (1) impute all values as < cut-off value,
- (2) multiply impute plasma RNA HIV-1 values using a uniform distribution (1 to LLoQ),
- (3) set values to missing,
- (4) impute values as < cut-off value if the target was not detected in the assay and set values to missing if the target was detected.

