**8     Associated Documents**

**Attachment 1: Writing Team Roster**

**Attachment 2: Snapshot Algorithm (using cut-off of HIV-1 RNA 200 copies/mL)**

Condition (‘Week 24’ indicates Week 24 window/‘Week 20’ indicates Week 20 window)	Response	Reasons
1. If non-permitted change in background therapy prior to Week 24/Week 20	HIV1-RNA $\geq$ 200	Change in ART
2. If permitted change in background therapy prior to Week 24/Week 20 AND the latest on-treatment VL prior to/on the date of change is $\geq$ 200 copies/mL	HIV1-RNA $\geq$ 200	Change in ART
3. If non-permitted change in background therapy during Week 24/Week 20 
 
Last on-treatment VL during Week 24/Week 20 prior to/on the date of change <math>\geq</math> 200 copies/mL
 
Last on-treatment VL during Week 24/Week 20 prior to/on the date of change <200 copies/mL
 
No VL during Week 24/Week 20 prior to/on the date of change
 
	HIV1-RNA $\geq$ 200 HIV1-RNA < 200 HIV1-RNA $\geq$ 200	Data in window and HIV-1 RNA $\geq$ 200 copies/mL  Change in ART
4. If permitted change in background therapy during Week 24/Week 20 AND the last on-treatment VL prior to/on the date of change is $\geq$ 200 copies/mL 
 
This last on-treatment VL occurs prior to Week 24/Week 20
 
This last on-treatment VL occurs during Week 24/Week 20 but prior to/on the date of change
 
	HIV1-RNA $\geq$ 200 HIV1-RNA $\geq$ 200	Change in ART Data in window and HIV-1 RNA $\geq$ 200 copies/mL
5. If none of the above conditions met 
 
VL available during Week 24/Week 20                             
 
Last on-treatment VL during Week 24/Week 20 <math>\geq</math> 200 copies/mL
 
Last on-treatment VL during Week 24/Week 20 < 200 copies/mL
 
 
 
No VL during Week 24                             
 
If subjects still on study (i.e. IP has not been permanently stopped up to Week 24)
 
If subjects withdraw before/during Week 24 due to
 
 
 
	HIV1-RNA $\geq$ 200 HIV1-RNA < 200 No virologic data at Week 24 Window	Data in window and HIV-1 RNA $\geq$ 200 copies/mL  On study but missing data in window

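### Among the LLoQ sensitivity analyses for virologic failure, (3) and (4) usually repeat the failure count of (1), and none uses target detection in that count

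*SAP*

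**What the plan says.** The virologic outcomes in SAP section 6.2.2 are HIV-1 RNA at or above 50 and at or above 200 copies/mL by the snapshot algorithm. Under the sub-heading on the lower limit of quantification, a result reported as below the LLoQ "will be imputed as lower limit of quantification (LLoQ) – 1". When an assay's LLoQ lies above the cut-off, with 60 copies/mL as the example, the plan adds four alternatives:

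- Analysis (1) makes each of these results a non-failure.
- Analysis (2) will "multiply impute plasma RNA HIV-1 values using a uniform distribution (1 to LLoQ", and it makes no exception for a target that was not detected.
- Analysis (3) discards each of these results as missing.
- Analysis (4) keeps not-detected results below the cut-off, but it will "set values to missing if the target was detected".

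On missing values, the estimand table says: "Missing data will be handled as described in the snapshot algorithm". In Attachment 2, condition 5, a participant still on study with no viral load in the window is put in a no-virologic-data category with the reason "On study but missing data in window". The regulatory examples that follow confirm that a high value before the window does not change this.

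**The concern.** The four analyses are meant to show how far the failure proportion depends on the handling of results that the assay cannot place on one side of the cut-off. Target detection is the one piece of assay information that separates possible low-level viraemia from a clearly suppressed result, and (4) was evidently written to use it. If missing and below the cut-off both count as non-failure, (4) cannot show its effect on the failure proportion, and (3) adds nothing to (1). Analysis (2) does move the count, but it gives not-detected results a chance of failure that (4) rules out. The report would then lack an analysis between the extremes that reflects what the assay says. Under the Supplementary Analyses of section 6.2.2, the same set is applied again to all treated participants.

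**Working it through.** The SAP gives no figure for these analyses, so there is none to reproduce.

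**Inputs from the SAP.** Cut-off 50; example LLoQ 60; base value LLoQ − 1; analyses (1) to (4); snapshot condition 5; about 70 participants in the primary analysis set (section 4).

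**Assumed for illustration.** One genuine failure; five results below 60, two with target not detected and three detected. Each is the only viral load in the window of a participant still on study. All 70 stay in the denominator.

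**Step 1: base rule.** 60 − 1 = 59, which is at or above 50, so every such result is a failure. This holds for any whole-number LLoQ above the cut-off (51 gives 50).

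**Step 2: probability of failure under (2).** For a uniform draw from 1 to LLoQ, P(failure) = (LLoQ − 50)/(LLoQ − 1):

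- LLoQ 60: 10/59 = 0.169
- LLoQ 75: 25/74 = 0.338
- LLoQ 100: 50/99 = 0.505

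This applies equally to detected and not-detected results.

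**Step 3: pass each rule through the snapshot.**

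| Analysis | Not detected (2) | Detected (3) | Failures of 70 |
|---|---|---|---|
| Base | failure | failure | 1 + 5 = 6 (8.6%; exact 95% CI 3.2 to 17.7%) |
| (1) | non-failure | non-failure | 1 (1.4%; CI 0.0 to 7.7%) |
| (2) | 0.169 each | 0.169 each | 1 + 5 × 10/59 = 1.85 expected (2.6%) |
| (3) | no virologic data | no virologic data | 1 (1.4%) |
| (4) | non-failure | no virologic data | 1 (1.4%) |

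Of the 0.85 failures that (2) adds, 2 × 10/59 = 0.34 come from not-detected results.

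**Step 4: range.** With 1 to 10 such results, the base rule gives 2 to 11 failures (2.9% to 15.7%), while (1), (3) and (4) stay at 1. Analysis (2) runs from 1.17 expected failures (one result, LLoQ 60) to 6.05 (ten results, LLoQ 100).

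**Step 5: where the tie breaks.**

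- *Earlier value in the window.* With 80 and then a result below 60, (1) gives below 50. Under (3), and under (4) if the target was detected, 80 becomes the last available value and the participant is a failure.
- *Denominator.* If participants without virologic data are left out, the proportions are (1) 1/70 = 1.43%, (3) 1/65 = 1.54% and (4) 1/67 = 1.49%. This shift comes only from removing non-failures.
- *Missing-data analyses.* If values set to missing enter the worst case under Missing Data in section 6.2.2, failures are (1) 1, (3) 6 and (4) 4.

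**Step 6: the alternative.** If (4) counts detected results as failures, it gives 1 + 3 = 4 of 70 (5.7%; CI 1.6 to 14.0%). If the draws in (2) are limited to detected results, (2) gives 1 + 3 × 10/59 = 1.51 expected (2.2%). As the assumed number detected goes from 0 to 5, the reworded (4) runs from 1/70 to 6/70, that is, from the value of (1) to that of the base rule.

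**The case against.** A reader might infer that the set fails to test the LLoQ assumption, or that three agreeing analyses would pass for evidence of robustness. The SAP supports neither. The assumption under test is LLoQ − 1, which makes every such result a failure, and (1) is the exact opposite. The two bracket every possible count and (2) lies between them. All four analyses depart from the base result (6/70 against 1/70 or 1.85/70 in the illustration), so the report would show a visible gap, not agreement.

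The equality is also not absolute. An earlier in-window value can break it. The general denominator rule in section 5 leaves out a missing category, without saying whether that covers participants with no virologic data. The analysis-approach entry of this estimand table could not be read in the copy at hand; that is no fault of the plan, but it leaves the denominator unconfirmed. The Missing Data paragraph applies multiple imputation and best and worst cases to missing study visits. If measured values set to missing were included, the worst case of (4) would equal the reworded (4). The SAP does not say that they are.

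Finally, (4) does use detection: it changes who is classed as below the cut-off and who has no data. And exempting not-detected results from the draws in (2) is a modelling choice.

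All of this narrows the point. It leaves standing that, with one in-window value and the snapshot alone, detection does not affect the failure count, and that (2) and (4) treat not-detected results inconsistently.

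**Conclusion.** The point holds in a limited form. For a participant on study with a single in-window result below an LLoQ that exceeds the cut-off, (3) and (4) reproduce the failure count of (1) under the snapshot alone. Analysis (2) gives not-detected results a 17% chance of failure at LLoQ 60 and cut-off 50. The base rule and (1) bracket the count, but no intermediate analysis uses detection in the numerator.

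The size in practice is unknown: the SAP gives an example LLoQ of 60 but not how often such assays occur or how often the target is detected. The illustrative counts rest on those assumptions and on a denominator of 70. The point concerns sensitivity analyses of a secondary endpoint, and only assays with LLoQ above the cut-off; for the 200 copies/mL outcome that would need an LLoQ above 200. Low priority, but cheap to put right.

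**What to change.** - In (4), count target-detected results as at or above the cut-off and not-detected results as below it. Present this as the upper bound given assay detection. It is not the overall maximum, which is the base rule.
- In (2), draw from the uniform distribution only for target-detected results and set not-detected results below the cut-off.
- Dropping (3) is optional. If it is kept, state whether its missing values stay in the denominator and whether they enter the multiple imputation and the best and worst cases under Missing Data.

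In the illustration the analyses would then be ordered (1) 1, (2) 1.51 expected, (4) 4 and base 6 failures of 70.

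The cost is a few lines of SAP text and code, since (4) already requires detection status. The one small downside is that (4) will look less favourable.
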